### **7.11. Adverse Event, Serious Adverse Event, and Adverse Event of Special Interest Reporting Requirements**

Each patient must be carefully monitored for the development of any AEs. This information must be obtained in the form of non-leading questions (e.g. “How are you feeling?”) and from signs and symptoms detected during each examination, observations of study personnel, and spontaneous reports from patients.

All AEs (serious and non-serious) spontaneously reported by the patient and/or in response to an open question from study personnel or revealed by observation, physical examination or other diagnostic procedures must be recorded. When possible, signs and symptoms indicating a common underlying pathology must be noted as 1 comprehensive event. Accompanying signs or symptoms (e.g. abnormal laboratory values) must not be reported as additional AEs. If a diagnosis is unknown, one or more symptoms may be reported as separate AEs. If an underlying diagnosis is subsequently determined for the reported symptom(s), then the reported symptom(s) term(s) must be revised to be “attributed” or “due” to the diagnosis.

All SAEs and AESIs that occur within the reporting period, regardless of causality, must be reported by the Investigator to Sponsor or designee **within 24 hours** from the point in time when the Investigator becomes aware of the SAE or AESI. SAEs and AESIs must be followed until resolution, the condition stabilizes, or the Investigator and Sponsor agree that follow up is not required. For the purposes of study analysis, if the event has not resolved at the end of the study reporting period, it must be documented as ongoing. For purposes of regulatory safety monitoring, the Investigator is required to follow the event to resolution and report to the Sponsor the outcome of the event. Further instructions on reporting of SAEs will be provided in the Study Reference Manual.

If there are serious unexpected suspected adverse drug reactions (SUSARs) associated with the use of the study drug, the Sponsor or authorized designee will ensure that the appropriate regulatory agencies and all participating investigators are notified on an expedited basis. In addition, the Sponsor or authorized designee will be responsible for notification of SUSARs to the ethics committees. It is the responsibility of the Investigator to promptly notify the local IRB/IEC/REB of SUSARs according to the institutional policy. An unexpected event is one that is not reported in the IB.

### **7.12. Abuse, Misuse, Overdose, and Medication Error**

Occurrences of events of overdose, drug misuse, drug abuse and medication error must be reported to the Sponsor.

**Abuse of a medicinal product:** Persistent or sporadic, intentional excessive use of medicinal products, which is accompanied by harmful physical or psychological effects [DIR 2001/83/EC Art 1(16)].

**Misuse:** Intentional and inappropriate use of a medicinal product not in accordance with the prescribed or authorized dose, route of administration, and/or the indication(s) or not within the legal status of its supply.

**Overdose:** Administration of a quantity of study drug given per administration or per day, which is above the assigned dose.

**Medication Error:** An error made in prescribing, dispensing, administration, and/or use of the study drug. Medication errors are reportable to the Sponsor as defined below.

- The dispensing, administration and/or use of the unassigned study drug.
- The administration and/or use of an expired study drug.

Note: Cases of patients missing doses of the study drug are not considered reportable as medication errors.

AEs or SAEs associated with drug abuse, misuse, overdose, or medication error must be reported as appropriate (Section 7.1 and Section 7.8).

## **8. WITHDRAWAL AND REPLACEMENT OF PATIENTS**

### **8.1. End of Treatment**

A patient is free to withdraw from the study drug treatment for any reason and at any time without giving reason for doing so and without penalty or prejudice. The Investigator is also free to terminate a patient's study drug treatment at any time if the patient's clinical condition warrants it. The primary reason for discontinuation or withdrawal of a patient from the study drug must be determined using the following categories:

- Clinical progression
- Progressive Disease by Independent Radiologic Review
- Progressive Disease by Investigator Assessment
- AE
- Withdrawal by patient from treatment
- Death
- Lost to Follow Up
- Non-compliance with study drug
- Physician decision
- Pregnancy
- Termination of Study by Sponsor
- Any other reason that in the opinion of the Investigator, would justify removing the patient from the study drug, based on the best interest of the patient

### **8.2. End of Study**

The primary reason for discontinuation or withdrawal of a patient from the study must be determined using the following categories:

- Death
- Lost to Follow Up
- Termination of Study by Sponsor
- Withdrawal by patient from Study
- Any other reason that in the opinion of the Investigator, would justify removing the patient from the study, based on the best interest of the patient

If a patient voluntarily withdraws from the study, the Investigator should attempt to contact the patient to determine the reason(s) for discontinuation and request the patient return for an EOT Visit and Safety Follow up Visit. If a patient withdraws from the study for any reason other than withdrawal by the patient, an EOT Visit and Safety Follow up Visit must be conducted, and the patient must be followed for OS and PFS2. Patients must return all used, partially used, and unused study drug bottles.

### 8.3. Replacement of Patients

Patients will not be replaced in this study.

## 9. STATISTICAL CONSIDERATIONS

### 9.1. Determination of Sample Size

The sample size selection of 426 patients (n=213 DCC-2618, n=213 sunitinib) was based on considerations for powering of the primary endpoint, secondary endpoints, detection of rare safety events and overall exposure to DCC-2618. Patients will be randomized in a 1:1 ratio of DCC-2618 versus sunitinib.

Under the assumptions that mPFS is 9 months for DCC-2618 and 6 months for sunitinib, the HR is about 0.667 for All Patients (AP) PFS (sunitinib vs DCC-2618). A total of 262 events will be required to achieve a statistical power of 90% to test the hypothesis of no difference between DCC-2618 and sunitinib in AP. Accrual of 426 patients (213 in DCC-2618 and 213 in sunitinib) within 21 months is expected to have 262 PFS events occurred after additional 8 months of follow up. This has accounted for 20% of dropout rate (discontinuation without progressive disease per IRR or death).

It is further assumed that the mPFS is 9 months for patients with a KIT Exon 11 primary mutation (Ex11) in DCC-2618 and 5 months for KIT Ex 11 in sunitinib, the HR is 0.556 for the KIT Exon11 PFS. It is planned to perform the final analysis on both KIT Ex11 and AP populations at the same time. The final analysis is planned to occur when at least 151 PFS events in KIT Ex11 population and approximately 262 PFS events in AP population have occurred. The 151 PFS events in KIT Ex11 population have at least 95% power to test the hypothesis of no difference between DCC-2618 and sunitinib in KIT Ex11 population.

### 9.2. Analysis Endpoints

#### 9.2.1. Primary Endpoint

The primary and secondary efficacy endpoints will be analyzed for both the Ex11 ITT and AP ITT populations (see Section 9.3).

##### 9.2.1.1. Efficacy

PFS based on independent radiologic review using modified RECIST (mRECIST) (Appendix 17.1). mRECIST criteria includes:

- No lymph nodes chosen as target lesions; enlarged lymph nodes followed as non-target lesions;
- No bone lesions chosen as target lesions;
- PET not acceptable for radiological evaluation;
- A progressively growing new tumor nodule within a pre-existing tumor mass must meet the following criteria to be considered as unequivocal evidence of progression according to the modification of RECIST Version 1.1: (a) the lesion is at least 2 cm in size and definitively a new active GIST lesion (e.g. enhancing with contrast or other criteria to rule out artefact); or (b) the lesion has to be expanding on at least 2 sequential imaging studies.

## 9.2.2. Key Secondary Endpoints

### 9.2.2.1. Efficacy

- ORR (confirmed CR + confirmed PR) based on independent radiologic review using mRECIST criteria
- OS

### 9.2.2.2. Other Secondary Endpoints

- QOL as measured by using EORTC QLQ-C30, DLQI, and the GP5 question from FACT-G
- TTP
- Disease control rate (DCR; CR + PR + SD) at 6, 9 and 12 months, based on independent radiologic review
- PFS based on investigator assessment
- Efficacy using Choi criteria based on independent radiologic review

#### 9.2.2.2.1. Safety

Safety endpoints that will be evaluated include treatment-emergent adverse events (TEAEs), AESIs, SAEs, dose reduction or discontinuation of study drug due to toxicity; and changes from baseline in ECOG PS, vital signs, ECGs, LVEF, dermatologic examinations, and clinical laboratory parameters.

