## **5.4. Study Drug Dose Interruption and Modification**

Sunitinib dose interruption and modification will follow guidelines as per the approved package insert or institutional guidelines. PK-guided sunitinib dosing is not allowed. Upon resumption following a dose interruption, the Investigator must continue with the patient's original visit schedule calculated from Cycle 1 Day 1 (i.e. cycle day count is continuous and does not pause with a dose interruption). Clinic visits and assessments should continue during dose interruptions as per [Table 1](#) (schedule of assessments). Dose interruptions of longer than 28 consecutive days will result in the patient being discontinued from the study. If the patient is on 4 weeks on, 2 weeks off cycle, the 28 days is inclusive of the 2 weeks off.

DCC-2618 may be interrupted or modified (i.e. dose reduction) at the discretion of the Investigator at any time due to AE, to accommodate palliative treatment, or for other reasons after consultation with the Sponsor. An interruption must be limited to no more than 28 consecutive days. Upon resumption following a dose interruption, the Investigator must continue with the patient's original visit schedule calculated from Cycle 1 Day 1 (i.e. cycle day count is continuous and does not pause with a dose interruption). Clinic visits and assessments should continue during dose interruptions as per [Table 1](#) (schedule of assessments). Dose interruptions of longer than 28 consecutive days will result in the patient being discontinued from the study.

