**Table 10: DCC-2618 Dose Modifications for Treatment Related Adverse Events Not Mentioned Above**

Toxicity Grade	Management Guideline
Any Grade 3 or 4	Interrupt DCC-2618 dosing until event has resolved to Grade 1 or baseline Once the AE returns to Grade 1 or baseline, reduce DCC-2618 by 1 dose level If a patient tolerates the reduced dose without recurrence of the event for at least 28 days, consider re-escalating the dose of DCC-2618 to the prior dose level
Asymptomatic/Not clinically significant Grade 3 or 4 laboratory AEs (including CPK and lipase) that persist ≤10 days	Closely monitor for clinical symptoms and continue DCC-2618 at the current dose level. Repeat labs within 10 days.
Asymptomatic/Not clinically significant Grade 3 or 4 laboratory AEs (including CPK and lipase) that persist >10 days	Closely monitor for clinical symptoms; for Grade 4 events, interrupt DCC-2618 until the event returns to Grade 3 Asymptomatic Grade 3 or Grade 4 elevations of plasma enzyme: lipase or CPK do not require dose interruption Once the AE returns to Grade 3, resume DCC-2618 at the current dose level or consider reducing by 1 dose level per Investigator discretion after discussion with the Sponsor.
Clinically Significant Grade 3 or 4 laboratory AEs (including CPK and lipase)	Interrupt the DCC-2618. If the Investigator assesses that restarting DCC-2618 is in the patient's best interest, the Sponsor must be contacted for discussion and determination if restarting is allowed.

AE=adverse event; CPK=creatinine phosphokinase

 The rules for dose modifications for laboratory AEs will be based on local laboratory results.

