### 7.4. Study Drug Action Taken

The Investigator must classify the study drug action taken with regard to the AE. The action taken must be classified according to the categories shown in [Table 14](#).

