**Table 14: Classification for Study Drug Action Taken with Regard to an Adverse Event**

Classification	Definition
Dose Not Changed	Study drug dose not changed in response to an AE.
Dose Reduced	Study drug dose reduced in response to an AE.
Drug Interrupted	Study drug administration interrupted in response to an AE.
Drug Withdrawn	Study drug administration permanently discontinued in response to an AE.
Not Applicable	Action taken regarding study drug administration does not apply. "Not applicable" must be used in circumstances such as when the study drug had been completed before the AE began and no opportunity to decide whether to continue, interrupt, or withdraw study drug is possible.

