## **9.8.6. Safety Analysis**

### **9.8.6.1. Adverse Events**

AEs will be summarized utilizing the number of events and proportion of patients overall, by system organ class (SOC) and preferred term for the Safety population. All tables will only include TEAEs, where treatment emergent is defined as any AE that occurs after administration of the first dose of study drug and through 30 days after the last dose of study drug, but data listings will include all collected AEs.

AE toxicity grade will be classified using NCI-CTCAE Version 5.0 criteria (See [Table 12](#)). If a patient has multiple occurrences of the same SOC or preferred term, then only the most severe event will be summarized in the tables for that SOC and preferred term. AEs of  $\geq$  Grade 3 will also be summarized. A missing toxicity grade will not be imputed.

The AE analysis will be repeated for SAEs, AEs leading to dose reduction or discontinuation, and AESIs.

No formal hypothesis-testing analysis of AE incidence rates will be performed.

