Adverse events of special interest (AESI) are serious or nonserious AEs of scientific and medical concern specific to study drug, for which ongoing monitoring and immediate notification by the Investigator to the Sponsor is required. AESIs will be flagged on the eCRF by the investigator. The following AEs are considered AESIs: squamous cell carcinoma (SCC) of skin, actinic keratosis, and keratoacanthoma.

The number and percentage of patients by treatment arm with the following categories of TEAEs will be summarized in tables by SOC and preferred term:

- Any AE
- Any AE by maximum severity grade

CONFIDENTIAL Page 25 of 29

- Any AE by maximum severity grade 1/2, 3/4, and 5
- Any drug-related AE
- Any SAE
- Any drug-related SAE
- Any AE leading to dose modification (dose reduction and dose interruption) or treatment discontinuation
- Any drug-related AE leading to dose modification or treatment discontinuation
- Any AESI
- Any AESI by maximum severity grade
- Any drug-related AESI
- Any fatal AE

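### The SAP never shows AE-related dose reductions on their own, although the protocol names them as a safety endpoint, and the coding of a sunitinib schedule change is left undefined

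*Protocol*

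**What the plan says.** **Endpoint.** Protocol Section 9.2.2.2.1 names "dose reduction or discontinuation of study drug due to toxicity" as a safety endpoint. Protocol Section 9.8.6.1 repeats the AE analysis for "AEs leading to dose reduction or discontinuation, and AESIs". Neither mentions interruption.

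**SAP tables.** SAP Section 1 states that the SAP takes precedence over the protocol's statistical sections. The list of by-SOC/PT tables in SAP Section 9.2 has the category "Any AE leading to dose modification (dose reduction and dose interruption) or treatment discontinuation". The text before that list keeps discontinuation apart from dose modification but does not split dose modification. SAP Section 9.1 counts patients who had a dose reduction and does not tie the reduction to an AE.

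**Recording.** Protocol Section 7.4 says: "The Investigator must classify the study drug action taken with regard to the AE". Table 14 then gives five codes for both arms: Dose Not Changed, Dose Reduced ("Study drug dose reduced in response to an AE"), Drug Interrupted ("Study drug administration interrupted in response to an AE"), Drug Withdrawn and Not Applicable. No code refers to a change of schedule.

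**How the two drugs are modified.** DCC-2618 (ripretinib in the SAP) is dosed continuously, with fixed reduction steps and toxicity tables. Sunitinib modification is left to the package insert or local guidelines. Protocol Section 5.3 asks sites to try to hold the 4/2 schedule through cycle 1, and Section 5.4 is conditional: "If the patient is on 4 weeks on, 2 weeks off cycle, the 28 days is inclusive of the 2 weeks off".

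**The concern.** Comparing the safety profiles of the two drugs is a stated secondary objective, and how often toxicity forces a lower dose or a stop is one of its direct tolerability measures. If the SAP is run as written, a reader of the study report will find AE-related discontinuations by arm but no count of AE-related reductions. In their place stands a figure that adds interruptions, which the protocol endpoint does not include.

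The substitution matters more here than in a trial of two continuous regimens. The arms differ in how many days there is a dose to interrupt, and only the sunitinib arm has an on/off schedule that can be altered without altering the daily dose. If sites code that alteration in different ways, the sunitinib count of reductions or interruptions depends partly on site habit.

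**Working it through.** The plan states no figure for this endpoint, so the check sets the passages side by side and adds short supporting arithmetic.

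**1. Which planned table gives which component?**

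| Component | Protocol 9.2.2.2.1 and 9.8.6.1 | SAP 9.2 overall summary | SAP 9.2 table list | SAP 9.1 |
|---|---|---|---|---|
| AE-related reduction | named | pooled with interruption | pooled with interruption and discontinuation | reductions of any cause only |
| AE-related interruption | not named | pooled with reduction | pooled | none |
| AE-related discontinuation | named | separate | pooled | none |

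No cell on the SAP side holds AE-related reduction alone, so reduction-or-discontinuation due to toxicity cannot be read from the planned output.

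**2. Why the pooled figure is not a neutral substitute.** Dosing days per 42-day cycle are 42 on ripretinib and 4 × 7 = 28 on sunitinib 4/2, which leaves 42 − 28 = 14 days with no dose to hold. The 28-day limit on interruptions counts the planned break on sunitinib, so the unplanned gap it allows is 28 days on ripretinib and 28 − 14 = 14 days on sunitinib 4/2. The pooling rule is the same in both arms, but the opportunity for an interruption is not.

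**3. Would relative dose intensity (RDI) reveal a schedule change?** SAP Section 9.1.2 defines sunitinib cycle RDI as the dose received divided by 50 × 7 × 4 = 1400 mg.

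- Planned 4/2: 28 days × 50 mg = 1400 mg, and 1400/1400 = 100%.
- Any other arrangement with 28 dosing days at 50 mg in 42 days: 1400/1400 = 100%. An assumed example, for arithmetic only, is two blocks of 2 weeks on and 1 week off: 14 + 14 = 28 dosing days.

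The daily dose is unchanged, so the reduction count does not register the change either. It appears in an AE table only if the site chose Dose Reduced or Drug Interrupted rather than Dose Not Changed.

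**4. How far could coding alone move the sunitinib figure?** The documents give no frequency, so this is an assumed range. Take 213 patients per arm, all dosed. Let a share *m* of sunitinib patients have a schedule change as their only action. The sunitinib rate then moves by *m* according to whether the code used is counted. For *m* = 0, 5, 10 and 15 points that is 0, 11, 21 and 32 of 213 patients. With true rates *p* of 20% to 40%, the 95% half-width of the difference between arms, 1.96 × √[(p(1−p) + (p−m)(1−p+m))/213], lies between 6.1 and 9.3 points. Coding would be minor at the low end of the range and comparable with sampling error at the upper end.

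**5. Can one AE carry two actions?** Yes. Protocol Table 10 calls for an interruption and then says: "Once the AE returns to Grade 1 or baseline, reduce DCC-2618 by 1 dose level". Table 8 (Grade 3) and Table 9 follow the same pattern. In the SAP's pooled category such an AE is counted under either code. Once the rows are split, it is counted correctly only if both actions are stored.

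**The case against.** The strongest reply is that the SAP is entitled to modify the protocol's plan, that it applies one rule to both arms, and that adding interruptions gives a broader tolerability measure. Discontinuation has a single code in both arms and its own summary, and reductions of any cause are counted in SAP Section 9.1. All of that stands. A reader might infer that the whole endpoint is missing or is measured differently by arm. The documents do not support that: the gap is the AE-related reduction component.

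Other tempting readings also go too far:

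- **Schedule changes vanish from every summary.** No passage describes a sunitinib schedule change at an unchanged dose; it is inferred from Protocol Sections 5.3 and 5.4. A site could enter it as Drug Interrupted, which the SAP tables would count. The coding is undefined, not impossible. Protocol Section 6.11.10 promises separate AE completion guidelines, which are not available here and might settle it.
- **One of two actions is always lost.** Section 7.4 is worded in the singular, but nothing limits the form to one code per AE.
- **The pooled figure is biased against ripretinib, by up to one third of holds (14/42).** That needs AEs to start evenly over the cycle, at equal rates in the two arms, and none to delay the restart after the break. The documents support none of this, and fewer dosing days is a feature of the comparator regimen.

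Finally, Protocol Section 9.8.6.1 rules out formal testing of AE rates, so alpha, power and the efficacy endpoints are untouched.

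**Conclusion.** The point holds in a limited form. The protocol and SAP disagree on a named safety endpoint, and under the SAP its reduction component is not produced by arm. This follows from the text alone and needs no assumption beyond taking the two documents supplied as the ones in force.

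The second part, undefined coding of a sunitinib schedule change, rests on an inference from Protocol Sections 5.3 and 5.4 and on the absence of a rule in Table 14. The result that RDI stays at 100% holds only where 28 dosing days at 50 mg are kept. The size of any effect is unknown; the 0 to 15 point range is illustrative. No direction of bias should be claimed. The consequence is confined to a descriptive safety comparison, which is still a stated objective, so the plan should be corrected.

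**What to change.** **SAP Section 9.2.** Tabulate by arm, in separate rows, TEAEs leading to dose reduction, to interruption and to discontinuation. Report the protocol endpoint as reduction or discontinuation. The pooled dose-modification row can stay as an extra. State what counts as a dose reduction in each arm.

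**Protocol Table 14 or the eCRF completion guideline.** Name one code for a toxicity-driven schedule change at an unchanged daily dose, and show such changes in their own row. Allow more than one action per AE; without this, the split rows could undercount AEs that led first to an interruption and then to a reduction.

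**AEs already entered.** Re-derive actions from dosing records only if the reasons for each change were collected. Neither document describes a dosing log with reasons. If there is none, say in the study report which period used the old coding.

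**Cost.** A few extra table rows, guideline wording, possibly one added eCRF option, and some recoding. No dose or clinical rule changes.

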### **9.8.6.2. Eastern Cooperative Oncology Group Performance Status**

Baseline, post baseline, and change at post baseline from baseline values will be summarized by time point utilizing descriptive statistics. No formal hypothesis-testing analysis will be performed.

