1. INTRODUCTION

This Statistical Analysis Plan (SAP) describes the detailed methodology for summary and statistical analyses of data from clinical protocol DCC-2618-03-002 (INTRIGUE) based on Amendment 6 of the study protocol, dated 23 October 2020. This document may modify the plans outlined in the protocol and supersedes the previous versions of the SAP and the statistical sections of the protocol.

Populations for analysis, statistical methods, data handling rules, and formats for data presentation are described within this document. The statistical analyses and summary tabulations described in this SAP will provide the basis for the results sections of the Clinical Study Report (CSR) for this trial. Analysis plan of population pharmacokinetics (PK) and exposure-response analysis, pharmacodynamics data, and quality-of-life (QOL) data collected for exploratory objectives will be separately documented.

Any changes to the data analysis methods after the SAP is finalized will be described in the CSR.

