3.2. Study Visits

All study assessments will be performed according to the schedule of assessments in the protocol. In general, for by-visit summaries, data recorded at nominal visits will be presented. Unscheduled visits will be mapped to a scheduled visit if possible, using a window based on all the available actual visit dates for the scheduled visits.

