3.6. General Analysis Conventions

Continuous data will be summarized using descriptive statistics (number of patients with assessment, mean, median, standard deviation, minimum, and maximum). Categorical data will be summarized using frequencies and proportions. Time-to-event data will be reported in months, and summarized via Kaplan-Meier (KM) methodology using the 25th, 50th (median), and 75th percentiles with associated 2-sided 95% confidence intervals (CIs), and time point survival probabilities with associated 2-sided 95% CIs.

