9.4. Eastern Cooperative Oncology Group Performance Status

The Eastern Cooperative Oncology Group (ECOG) Performance Status Assessments will be summarized as a categorical variable at each visit.

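### The SAP tabulates ECOG performance status only as categories by visit, so the protocol's safety endpoint of change from baseline in ECOG PS is not produced

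*Protocol*

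**What the plan says.** Protocol Section 9.2.2.2.1 lists, among the safety endpoints, "changes from baseline in ECOG PS, vital signs, ECGs, LVEF, dermatologic examinations, and clinical laboratory parameters". The synopsis carries the same list. Protocol Section 9.8.6.2 then gives the analysis for ECOG: "Baseline, post baseline, and change at post baseline from baseline values will be summarized by time point utilizing descriptive statistics", with no hypothesis test.

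SAP Section 9.4 is a single sentence, whose operative part is "Performance Status Assessments will be summarized as a categorical variable at each visit". Under SAP Section 3.6, "Categorical data will be summarized using frequencies and proportions". Under SAP Section 3.2, "In general, for by-visit summaries, data recorded at nominal visits will be presented". Elsewhere the SAP uses ECOG only as a baseline characteristic (Section 7.1, screening score) and as a subgroup factor (Section 8.6, screening score).

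On precedence, SAP Section 1 allows the SAP to modify the protocol's plans and says that it "supersedes the previous versions of the SAP and the statistical sections of the protocol".

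On collection, the protocol's schedule of assessments (Table 1) marks ECOG at screening, at Days 1, 15 and 29 of Cycle 1, Days 1 and 29 of Cycle 2, Day 1 of each later cycle, and the end-of-treatment visit. Protocol Section 6.3 requires patients who stop early to attend that visit within 7 days of their last dose.

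**The concern.** An endpoint defined as a change needs two values from the same patient. The protocol names such an endpoint for ECOG and says how to summarise it. The document that controls the tables replaces it with a distribution at each visit and does not say that the change summary was dropped, or why.

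What is at stake is one part of the safety comparison, which is a stated secondary objective. Patients may enter with ECOG 0, 1 or 2 (inclusion criterion 5), so a post-baseline category means little without the starting value. A patient recorded at ECOG 1 may have entered at 1, fallen from 0 or improved from 2, and the planned table treats these alike.

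**Working it through.** The plan states no figure for this endpoint, and no sample size, event count or significance level bears on it. The check is a comparison of text, followed by a short logical test.

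**Step 1: does any SAP table give the named endpoint?** The items in the protocol's list compare with the SAP as follows.

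| Item in the protocol's list | What the SAP plans | Change measure kept? |
|---|---|---|
| Laboratory parameters | Numeric change, plus the largest movement in toxicity grade from baseline (9.5) | Yes |
| Vital signs | Change from baseline (9.6) | Yes |
| ECGs | Interval changes, plus categories of largest QTc change (9.7) | Yes |
| LVEF | Numeric change, plus a percent-reduction threshold (9.8) | Yes |
| Dermatologic examinations | Patients with new suspicious lesions (9.9) | In effect: new lesions are counted |
| ECOG PS | Categories at each visit (9.4) | No |

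ECOG is the only item left without a measure relative to the patient's own starting point.

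**Step 2: does the protocol's own text fill the gap?** No. Section 9.8.6.2 lies in the statistical part of the protocol, which the SAP supersedes.

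**Step 3: can the change be recovered from the planned table?** No. Frequencies at two visits are marginal totals, and many different sets of individual movements give the same totals. As a test of logic with assumed numbers: of 100 patients with ECOG 0/1/2 in 50/40/10, let ten move from 0 to 1 and ten from 1 to 0. The counts become 50 − 10 + 10 = 50, 40 + 10 − 10 = 40 and 10. The table is unchanged although ten patients worsened. This shows only that the table cannot identify worsening. It does not estimate how often worsening will occur.

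**Step 4: what about patients who stop?** A value is scheduled at the end-of-treatment visit, and a summary at each visit can reasonably be read to include it. That row gives the status of leavers when they stop, but as category counts not linked to baseline. It has the same limitation as in Step 3.

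**Step 5: would restoring the protocol's summary be enough?** Only in part. Change by time point would bring back the named endpoint, but each on-treatment time point would still describe only the patients then attending. A worst post-baseline shift that includes the end-of-treatment value takes one result per patient and deals with both matters.

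**The case against.** The case for leaving the SAP alone has real strength.

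- **The SAP may modify the protocol.** It says so. ECOG is an ordinal grade, and frequencies are a reasonable alternative to the mean changes that the protocol's wording could imply. This stands as a reason not to summarise ECOG by means. It does not explain why a change measure disappears altogether, since a shift table is also categorical.
- **Screening ECOG is tabulated by arm, so group change can be read off.** Only the net movement can be read, and later visits may contain fewer patients than the screening table.
- **Decline is reported elsewhere.** Reasons for stopping treatment are tabulated (SAP Section 5), and the protocol's categories include clinical progression, adverse event and death (Section 8.1). Deaths are tabulated by cause (SAP Section 9.3). Change in EORTC physical and role function is compared between arms at 3 and 6 months (SAP Section 8.3.3.1). This stands and limits the consequence, though none of these is the clinician-rated change that the protocol names.
- **A worst-value table exceeds what either document promised.** True. It is offered as the better way to deliver the endpoint, and not as something the protocol requires.

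A reader might go further and infer that patients who deteriorate and leave are hidden. The documents do not support that. An end-of-treatment ECOG value is scheduled, early stoppers must attend that visit, and reasons for stopping and deaths are reported. Nor does the limitation of by-visit rows to attending patients come from the SAP, because the protocol's own summary by time point shares it.

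**Conclusion.** The point holds as a minor gap in a descriptive safety analysis. The protocol names change from baseline in ECOG PS as an endpoint, and the governing SAP contains no table that gives it. Category counts by visit or at end of treatment cannot show within-patient worsening.

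No numerical size can be attached. The documents give no rate of ECOG deterioration in either arm, and the design medians of 9 and 6 months are PFS assumptions, which do not describe time on treatment or functional decline. A reader might infer from the difference in medians that the by-visit tables would mask a difference between arms. Any figure for that would rest on invented rates and would have to account for the end-of-treatment row.

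The protocol plans no ECOG hypothesis test, and ECOG change has no place in the testing hierarchy, so the primary analysis, alpha and power are unaffected. The conclusion assumes that the protocol text supplied matches the version on which the SAP is based. The SAP cites Amendment 6, and the protocol text supplied does not show its amendment number.

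**What to change.** In SAP Section 9.4, add by arm, in the Safety and Ex11 Safety populations:

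- a shift table from baseline ECOG to worst post-baseline ECOG, counting end-of-treatment and unscheduled values;
- the number and percentage of patients worsening by at least one level and by at least two levels, among those with a baseline and at least one post-baseline value;
- the number of patients with no post-baseline value.

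Use the baseline rule in SAP Section 3.4. Because Table 1 allows ECOG to be done before or after dosing, say which value serves as baseline when the Cycle 1 Day 1 assessment follows the first dose. Keep the by-visit table, with its denominators, as supportive. If the sponsor prefers not to add the table, the SAP should state that the ECOG change summary has been dropped and give the reason.

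The cost is a few lines of SAP wording and one extra table from data already scheduled for collection. No visit, assessment or test is added.
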